## 8 LIST OF TABLES AND TABLE SHELLS

This section presents an overview of the table shells.

**Table 2.** Descriptive statistics

Population	Subgroup	Outcome	Result
All included patients	-	Number of patients	N (100%)
		Age	Median, mean and st. deviation
All included patients	Patients younger than 50 years	Number of patients	N (%)
	Patients aged 50-70 years	Number of patients	N (%)
	Patients older than 70 years	Number of patients	N (%)
All included patients	Patients with visceral disease	Number of patients	N (%)
		Age	Median, mean and st. deviation
	Patients without visceral disease	Number of patients	N (%)
		Age	Median, mean and st. deviation
All included patients	Primary MBC	Number of patients	N (%)
		Age	Median, mean and st. deviation
	Recurrent MBC	Number of patients	N (%)
		Age	Median, mean and st. deviation

PFIZER CONFIDENTIAL

**Table 3.** Disease-specific descriptive statistics.

Population	Subgroup	Outcome	Result
All included patients	-	Type of metastases	Visceral: N (%) Non-visceral: N (%) Both: N (%)
		Number of metastases	0: N (%) 1: N (%) 2: N (%) >2: N (%)
		Location of metastases	Skin: N (%) Bone: N (%) Lung: N (%) Liver: N (%) CNS: N (%) Other: N (%)
		Surgery	Yes: N (%) No: N (%)
		Adjuvant treatment*	Type 1: Median number of treatments of type 1: Type 2: Median number of treatments of type 2:
All included patients	Patients younger than 50 years	Type of metastases	Visceral: N (%) Non-visceral: N (%) Both: N (%)
		Number of metastases	0: N (%) 1: N (%) 2: N (%) >2: N (%)
		Location of metastases	Skin: N (%) Bone: N (%) Lung: N (%) Liver: N (%) CNS: N (%) Other: N (%)
		Surgery	Yes: N (%) No: N (%)
		Adjuvant treatment*	Type 1: Median number of treatments of type 1: Type 2: Median number of treatments of type 2:

PFIZER CONFIDENTIAL

Patients aged 50-70 years	Type of metastases	Visceral: N (%) Non-visceral: N (%) Both: N (%)
	Number of metastases	0: N (%) 1: N (%) 2: N (%) >2: N (%)
	Location of metastases	Skin: N (%) Bone: N (%) Lung: N (%) Liver: N (%) CNS: N (%) Other: N (%)
	Surgery	Yes: N (%) No: N (%)
	Adjuvant treatment*	Type 1: Median number of treatments of type 1: Type 2: Median number of treatments of type 2:
Patients older than 70 years	Type of metastases	Visceral: N (%) Non-visceral: N (%) Both: N (%)
	Number of metastases	0: N (%) 1: N (%) 2: N (%) >2: N (%)
	Location of metastases	Skin: N (%) Bone: N (%) Lung: N (%) Liver: N (%) CNS: N (%) Other: N (%)
	Surgery	Yes: N (%) No: N (%)
	Adjuvant treatment*	Type 1: Median number of treatments of type 1: Type 2: Median number of treatments of type 2:

PFIZER CONFIDENTIAL

All included patients	Visceral metastases	Type of MBC	Primary MBC: N (%) Recurrent MBC: N (%)
		Number of metastases	0: N (%) 1: N (%) 2: N (%) >2: N (%)
		Location of metastases	Skin: N (%) Bone: N (%) Lung: N (%) Liver: N (%) CNS: N (%) Other: N (%)
		Surgery	Yes: N (%) No: N (%)
		Adjuvant treatment*	Type 1: Median number of treatments of type 1: Type 2: Median number of treatments of type 2:
Non-visceral metastases		Type of MBC	Primary MBC: N (%) Recurrent MBC: N (%)
		Number of metastases	0: N (%) 1: N (%) 2: N (%) >2: N (%)
		Location of metastases	Skin: N (%) Bone: N (%) Lung: N (%) Liver: N (%) CNS: N (%) Other: N (%)
		Surgery	Yes: N (%) No: N (%)
		Adjuvant treatment*	Type 1: Median number of treatments of type 1: Type 2: Median number of treatments of type 2:
		Time from initial breast cancer diagnosis (incidence date) to relapse	Median time

\* The result may be more than 2 types of adjuvant treatment.

PFIZER CONFIDENTIAL

**Table 4.** Progression Free Survival (PFS)\*

Endpoint	Population	Subgroup	Outcome	Result
Primary	Included patients treated with palbociclib in combination with AI	-	PFS	Median and IQR
Primary	Included patients treated with palbociclib in combination with AI	Patients younger than 50 years	PFS	Median and IQR
		Patients aged 50-70 years	PFS	Median and IQR
		Patients older than 70 years	PFS	Median and IQR
Primary	Included patients treated with palbociclib in combination with AI	Patients with visceral disease	PFS	Median and IQR
		Patients without visceral disease	PFS	Median and IQR
Secondary	Included patients treated with palbociclib in combination with Fulvestrant	-	PFS	Median and IQR
Secondary	Included patients treated with palbociclib in combination with Fulvestrant	Patients younger than 50 years	PFS	Median and IQR
		Patients aged 50-70 years	PFS	Median and IQR
		Patients older than 70 years	PFS	Median and IQR
Secondary	Included patients treated with palbociclib in combination with Fulvestrant	Patients with visceral disease	PFS	Median and IQR
		Patients without visceral disease	PFS	Median and IQR

Table note: \* Following definition of PFS in section 7.1.

**Table 5.** Time on Treatment (ToT)\*

Endpoint	Population	Subgroup	Outcome	Result
Primary	Included patients treated with palbociclib in combination with AI	-	ToT	Median and IQR
Primary	Included patients treated with palbociclib in combination with AI	Patients younger than 50 years	ToT	Median and IQR
		Patients aged 50-70 years	ToT	Median and IQR
		Patients older than 70 years	ToT	Median and IQR
Primary	Included patients treated with palbociclib in combination with AI	Patients with visceral disease	ToT	Median and IQR
		Patients without visceral disease	ToT	Median and IQR
Secondary	Included patients treated with palbociclib in combination with Fulvestrant	-	ToT	Median and IQR
Secondary	Included patients treated with palbociclib in combination with Fulvestrant	Patients younger than 50 years	ToT	Median and IQR
		Patients aged 50-70 years	ToT	Median and IQR
		Patients older than 70 years	ToT	Median and IQR
Secondary	Included patients treated with palbociclib in combination with Fulvestrant	Patients with visceral disease	ToT	Median and IQR
		Patients without visceral disease	ToT	Median and IQR

Table note: \* Following definition of ToT in section 7.1.

**Table 6.** Overall Survival (OS)\*

Endpoint	Population	Subgroup	Outcome	Result
Secondary	Included patients treated with palbociclib in combination with AI	-	OS	Median and IQR OS-rates (%) at 6, 12 and 24-months
Secondary	Included patients treated with palbociclib in combination with AI	Patients younger than 50 years	OS	Median and IQR OS-rates (%) at 6, 12 and 24-months
		Patients aged 50-70 years	OS	Median and IQR OS-rates (%) at 6, 12 and 24-months
		Patients older than 70 years	OS	Median and IQR OS-rates (%) at 6, 12 and 24-months
Secondary	Included patients treated with palbociclib in combination with AI	Patients with visceral disease	OS	Median and IQR OS-rates (%) at 6, 12 and 24-months
		Patients without visceral disease	OS	Median and IQR OS-rates (%) at 6, 12 and 24-months
Secondary	Included patients treated with palbociclib in combination with Fulvestrant	-	OS	Median and IQR OS-rates (%) at 6, 12 and 24-months
Secondary	Included patients treated with palbociclib in combination with Fulvestrant	Patients younger than 50 years	OS	Median and IQR OS-rates (%) at 6, 12 and 24-months
		Patients aged 50-70 years	OS	Median and IQR OS-rates (%) at 6, 12 and 24-months
		Patients older than 70 years	OS	Median and IQR OS-rates (%) at 6, 12 and 24-months
Secondary	Included patients treated with palbociclib in combination with Fulvestrant	Patients with visceral disease	OS	Median and IQR OS-rates (%) at 6, 12 and 24-months
		Patients without visceral disease	OS	Median and IQR OS-rates (%) at 6, 12 and 24-months

Table note: \* Following definition of OS in section 7.1.

PFIZER CONFIDENTIAL

For PFS, ToT and OS (Table 4-6), unadjusted Kaplan Meier curves will be presented.

**Table 7.** First subsequent post-palbociclib treatment upon progression

[figure not shown]
Endpoint	Population	Subgroup	Outcome	Result
Secondary	All included patients treated	-	Treatment*	Type 1: Number of patients treated with type 1: Type 2: Number of patients treated with type 2:
Secondary	All included patients treated	Patients younger than 50 years	Treatment*	Type 1: Number of patients treated with type 1: Type 2: Number of patients treated with type 2:
		Patients aged 50-70 years	Treatment*	Type 1: Number of patients treated with type 1: Type 2: Number of patients treated with type 2:

PFIZER CONFIDENTIAL

		Patients older than 70 years	Treatment*	Type 1: Number of patients treated with type 1: Type 2: Number of patients treated with type 2:
Secondary	All included patients treated	Patients with visceral disease	Treatment*	Type 1: Number of patients treated with type 1: Type 2: Number of patients treated with type 2:
		Patients without visceral disease	Treatment*	Type 1: Number of patients treated with type 1: Type 2: Number of patients treated with type 2:

Table note: \* The result may be more than 2 types of treatment. "No subsequent treatment" is also possible.

PFIZER CONFIDENTIAL

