## 5 ENDPOINTS AND VARIABLES

[figure not shown]
*The primary endpoints of the study are:*

- *Progression-Free Survival (PFS) of patients receiving palbociclib in combination with aromatase inhibitor (AI)*
- *Time on Treatment (ToT) of patients receiving palbociclib in combination with AI*

*The secondary endpoints are:*

- *PFS of patients receiving palbociclib in combination with Fulvestrant*
- *ToT with palbociclib in combination with Fulvestrant*
- *Overall Survival (OS) in patients receiving palbociclib in combination with AI*
- *Overall Survival (OS) in patients receiving palbociclib in combination with Fulvestrant*
- *First subsequent post-palbociclib treatment upon progression*

PFIZER CONFIDENTIAL

- *Results in terms of disease-specific descriptive statistics describing the patients who have received Palbociclib:*
  - *Type, number and location of metastases (visceral vs. non-visceral)*
  - *Surgery*
  - *Type and number of adjuvant treatment(s)*
  - *De novo (primary MBC)*
  - *Recurrent MBC*
  - *Median time from initial breast cancer diagnosis (incidence date) to relapse (only relevant for recurrent MBC)*

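### SAP Table 3 reports adjuvant treatment only as a median number of treatments per type, so it cannot show what share of patients received each type

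*SAP*

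**What the plan says.** SAP section 5 lists the type and number of adjuvant treatments among the disease-specific secondary endpoints. Protocol sections 4 and 8 list the same item under disease characteristics.

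The result is specified in the Table 3 shell (SAP section 8). All six blocks (all patients, three age groups, visceral, non-visceral) carry the same cell: a label for the first type followed by "Median number of treatments of type 1", and the same pair again for the second type. The only footnote is "The result may be more than 2 types of adjuvant treatment".

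Other parts of the SAP are handled differently:
- **Other categorical rows of Table 3** are set out as counts with percentages. The type-of-metastases row, for example, begins "Visceral: N (%) Non-visceral: N (%) Both: N".
- **Table 7**, on first treatment after palbociclib, has the same layout but asks for patients: "Type 1: Number of patients treated with type 1".
- **Time from diagnosis to relapse** is marked in section 5 as "only relevant for recurrent MBC". The adjuvant item has no such note.

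The population column for Table 3 reads as all included patients. Primary (de novo) patients belong to that population: the register holds them (SAP section 2.2), and both Table 2 and the type-of-MBC rows of Table 3 count them.

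**The concern.** Two questions would be asked of this endpoint: how many patients had each kind of adjuvant therapy, and how much of it they had. A median number per type does not answer the first. For the second, its meaning depends on what is being counted and over whom, and the SAP states neither.

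De novo patients add to the difficulty. By the meaning of the terms (the documents do not say so), adjuvant treatment does not apply to disease that was metastatic at first diagnosis. If those patients stay in the calculation as zeros, the median mixes uptake among eligible patients with the proportion of patients who were never eligible.

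The study describes itself as purely descriptive, so its tables are its result. A listed endpoint that the shell cannot answer is a real, though contained, shortfall.

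**Working it through.** The plan states no figure on this point, so there is nothing to reproduce. The check is what the shell could convey under each reading of its undefined terms.

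**Inputs.** N = 1,500 is the expected population (SAP section 2.2; protocol section 9.5). Let d be the de novo share and p the share of recurrent patients who had a given adjuvant type. The documents give neither, so the values below are assumptions.

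**Reading 1: 0/1 count, all included patients.** The share treated overall is p(1 − d). The median is 0 when p(1 − d) < 0.5, that is, when d > 1 − 0.5/p:

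| p | d above which the median is 0 |
|---|---|
| 60% | 1 − 0.5/0.60 = 16.7% |
| 70% | 1 − 0.5/0.70 = 28.6% |
| 80% | 1 − 0.5/0.80 = 37.5% |

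With d = 30% and p = 70%, there are 1,500 × 0.70 = 1,050 recurrent patients, of whom 1,050 × 0.70 = 735 are treated. That is 735/1,500 = 49.0%, so the median is 0.

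The zero does not always occur:
- d = 30%, p = 80%: 1,050 × 0.80 = 840, or 56.0%; median 1.
- d = 20%, p = 65%: 1,200 × 0.65 = 780, or 52.0%; median 1.

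**Reading 2: 0/1 count, recurrent patients only.** Uptake of 1%, 25% or 49% gives a median of 0. Uptake of 51%, 75% or 99% gives 1. The cell says only which side of one half the uptake lies on.

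**Reading 3: only patients who had the type.** The median is at least 1 whatever the uptake, so it carries no information on uptake.

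**Reading 4: courses or cycles rather than 0/1.** The median then describes amount of treatment. Over all or all recurrent patients it is 0 when fewer than half were treated and positive when more than half were. The proportion itself is still not reported.

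Under all four readings, the share of patients who received each type cannot be read from the table. That result does not depend on p or d.

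**Source field.** Neither variable list (protocol section 9.3, SAP section 5.1) names a variable for adjuvant treatment.

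**The case against.** The best defence is SAP section 7.2, which promises numbers and percentages for the descriptive statistics, together with section 8 calling itself an overview. On that view an analyst would add the counts when programming the table. This has some force as a statement of intent. But section 7.2 points to the section 8 shells for presentation, and the adjuvant cell has no field for a count. Nor can the type label be taken as an implied count: Table 7 uses the same label and then asks for the number of patients separately.

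A second objection stands. A reader might infer that Table 3 will print 0 for a therapy that most recurrent patients had, or that subgroups with equal uptake will differ because their de novo shares differ. The documents do not support either as an expected result. Both need a 0/1 count, a denominator that includes de novo patients, and values of p and d that put p(1 − d) on the relevant side of one half. The population column does not settle the denominator: the time-to-relapse row in Table 3 has no recurrent-only label either, yet section 5 restricts that item. The de novo share is also not hidden throughout: Table 2 gives it overall, and Table 3 gives it for the visceral and non-visceral blocks. Only the age blocks lack it.

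Third, this is one row of a secondary table in a study without formal hypotheses. That limits the severity, but the endpoint still goes unanswered.

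**Conclusion.** The point holds in this form: the adjuvant row has no N (%) per type, no defined unit and no restriction to recurrent disease, so the table cannot report the share of patients who received each adjuvant type. This rests on the wording of the shell alone.

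The zero median at p = 70% and d = 30% is an illustration under assumed values. It shows that the statistic can mislead, not that it will.

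The missing variable is a related gap, but it should not be read as proof that the register lacks adjuvant data. Both lists are headed as main variables, so the field may exist without being named.

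The effect is confined to a secondary descriptive endpoint. PFS, time on treatment and OS are unchanged. The change is worth making before the tables are programmed, but it is not critical.

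**What to change.** In every block of SAP Table 3:
1. Add a line for each adjuvant type giving N (%), with recurrent MBC patients as the denominator, overall and in each subgroup. State that a patient may appear under more than one type.
2. Show de novo patients separately as not applicable.
3. Keep the number of treatments per type, since the endpoint includes number. Define the unit (for example regimens, courses or cycles) and report median and IQR among patients who received that type.
4. Name the source field for adjuvant treatment in the variable lists of SAP section 5.1 and protocol section 9.3.

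The cost is a few more table rows and confirmation with the register that the field is available. If it is not available in the form needed, the endpoint itself would have to be restated.
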